1.0 Introduction and Background

Taxane chemotherapies such as paclitaxel and docetaxel have had an increasing role in the treatment of breast cancer and are now used in the majority of patients receiving perioperative chemotherapy.¹ Taxanes exert their effect by excess stabilization of microtubules which disrupts the mitotic spindle of dividing cancer cells. However, healthy neuronal cells also rely on functional microtubules in their axons and dendrites for both structural support and transport of intracellular products. Disruption of these neuronal microtubules leads to a dose-dependent peripheral neuropathy that is the dose-limiting toxicity of taxanes.² Taxane-induced peripheral neuropathy (TIPN) initially tends to manifest as a progressively worsening sensory impairment which is often felt as painful paresthesias with decreased deep tendon reflexes; this may be followed by a delayed motor deficit causing distal weakness.³ TIPN is often reversible if it is intervened upon early enough with dose reduction or discontinuation of taxane treatments; if treatment is continued there is higher risk of irreversible symptoms.⁴ A retrospective clinical practice study of early-stage taxane-treated breast cancer patients found that 10% of them had dose-limiting TIPN; roughly half of whom had early discontinuation of treatment with an average 28% lower cumulative taxane dose than planned.⁵ When chemotherapy cannot be given as intended due to dose reductions it is generally associated with worse outcomes,⁶ suggesting that TIPN may have an indirect effect upon overall survival in some breast cancer patients.

TIPN manifests via several different pathophysiological mechanisms that can be assessed by current modalities; none of which have yet emerged as a widely-adopted standardized approach. Taxane disruption of microtubules impairs the normal self-maintenance of neurons which is evident structurally as the degeneration of distal axons and nerve terminals. Inflammatory changes occur as the innate immune system responds to these damaged and leaking organelles. Genetic polymorphisms in neuronal and inflammatory cells contribute to individual variability in TIPN vulnerability. Functionally, as a neuronal myelin sheath deteriorates it increases the membrane surface area through which current must flow, slowing electrical conduction velocity and weakening its signal amplitude. Finally, as a result of the above mechanisms, degradation and inflammation can alter large peripheral nerves to the point that gross anatomic changes are evident on imaging.

Ultrasound (US) is a non-invasive, non-irradiating, emerging imaging modality which can be used to assess peripheral nerves. Nerve fiber cross-sectional area (CSA), echogenicity, and vascularity are assessed and provide an indication of nerve health and potential pathology. The majority of US data have been published on detection of entrapment syndromes such as carpal tunnel syndrome. In these cases the most common US findings include nerve enlargement, decreased echogenicity proximal to the entrapment, and an increase in nerve vascularity.⁷ Other studies have found that US can detect other peripheral nerve lesions or neuropathies, with the most reliable finding a change in nerve CSA. Ultrasound measurements of the sensory sural nerve at the distal calf in healthy participants without neuropathy had an average CSA of 5.3 mm² with standard deviation 1.8 mm² for a normal reference range of 1.7-8.9 mm².⁸ Another ultrasound study assessed the sural nerve more distally at the ankle and found a smaller CSA which was significantly enlarged ($p < 0.001$) in patients with diabetic

A Pilot Study Using Ultrasound for the Detection of Taxane-Induced Peripheral Neuropathy
Wake Forest Baptist Comprehensive Cancer Center (WFBCCC)
CCCWFU # 97217

polyneuropathy as compared to healthy controls (mean/standard deviation 2.59 / 0.96 mm² as compared to 1.40 / 0.59 mm²).⁹

To date, there has only been one small study assessing US detection of chemotherapy-induced peripheral neuropathy; this was done among colorectal cancer patients who had received oxaliplatin. Similar to several other etiologies of nerve lesions/neuropathies, this study also found an increased peripheral nerve CSA compared to reference values. Interestingly, although the patients had denied symptoms of neuropathies at time of recruitment, this study found areas of increased peripheral nerve CSA at upper extremity sites of entrapment such as the carpal tunnel and ulnar groove; it did not find US abnormalities in terms of CSA or echogenicity at the sural nerve or other sites.¹⁰ Oxaliplatin has a much different mechanism of action from the taxanes; as a platinum-based agent it causes DNA cross-linking which inhibits cancer cell growth. Oxaliplatin-induced neuropathy is also a distinct entity that is characterized by cold sensitivity and mediated by prolonged opening of sodium ion channels along neuronal axons.¹¹ On a review of publications in the MEDLINE database as well as abstracts from the American Society of Clinical Oncology, we did not find any other prior studies that focused on the use of US to detect chemotherapy-induced peripheral neuropathy, and none for TIPN.

As noted above, there are currently several different diagnostic modalities that can assess TIPN, including self-reported symptoms, physical examination, nerve conduction study, sudometer testing, and skin biopsies. But each have limitations so that none have emerged as a widely-adopted standardized approach.

In routine practice, most clinicians rely on patients' self-reported symptoms alone for TIPN detection. These symptoms can be measured on one of several clinician-administered grading scales, although these have inter-scale and inter-observer variability.¹² The European Organization for Research and Treatment of Cancer (EORTC) QLQ-CIPN20 Questionnaire is a 20-item self-reported survey that is easy to administer and was validated across participants in four large cooperative group trials.¹³ Furthermore, although in many patients the development of acute TIPN symptoms is predictive of eventual chronic TIPN,¹⁴ some patients develop a disproportionately delayed TIPN that is not able to be self-reported early enough to allow for intervention.

The European Organization for Research and Treatment of Cancer (EORTC) QLQ-CIPN20 Questionnaire is a 20-item self-reported survey that is easy to administer and was validated across participants in four large cooperative group trials.¹³ The QLQ-CIPN20 sensory scale has been studied specifically with TIPN among breast cancer patients and was shown to be correlated with patient-reported symptoms from the Common Toxicity Criteria (0.79, $p < 0.00001$). Since taxanes are not associated with hearing loss, that corresponding item was excluded from analysis in that study.¹⁵ For normative comparison, non-cancer patients tend to have very low scores on the QLQ-CIPN20 with a sum score average of 3.6 (standard deviation 7.2) and subtotals of 3.2 (7.3) for sensory measures, 3.8 (9.2) for motor, and 4.4 (10.7) for autonomic. The vast majority of non-cancer patients (90.1%) had a sum score of 0-10%; older age and self-reported comorbidities were associated with higher QLQ-CIPN20 scores. Based on the results from that study, age-matched normative data has been generated for the QLQ-CIPN20.¹⁶

A Pilot Study Using Ultrasound for the Detection of Taxane-Induced Peripheral Neuropathy
Wake Forest Baptist Comprehensive Cancer Center (WFBCCC)
CCCWFU # 97217

Physical examination with quantitative sensory testing (QST) uses tuning forks or monofilaments to objectively measure the sensory threshold for proprioception. QST may be a useful addition to self-reported symptoms as it is non-invasive, easily implemented, and well-correlated with self-reported TIPN symptoms. Although promising, it has not been shown to provide early detection of subclinical TIPN.^{17,18}

Nerve conduction studies (NCS) measure impairment of electrical function in large peripheral nerves and are thought to be a sensitive and specific measure of TIPN. NCS measures amplitude and latency of neuronal signaling. Reduction in the conduction velocity within a peripheral nerve indicates damage to the myelin, while reduction in the amplitude indicates axonal damage. Typical NCS findings suggestive of TIPN include slowed conduction velocity at common sites of entrapment (such as the carpal tunnel) and an earlier reduction of sural sensory amplitude relative to the radial nerve.¹⁹ A prospective study of patients receiving paclitaxel and carboplatin found a reduction in sural nerve conduction from baseline in terms of the sensory action potential amplitude (14.5 +/- 9.0 uV to 9.7 +/- 7.1) and the sensory conduction velocity (54.6 +/- 7.7 m/s to 46.3 +/- 8.8).²⁰ A series of patients who received paclitaxel and cisplatin had a reduction in the sural nerve amplitude of sensory action potential from average 13.7 uV (standard deviation 6.5) to 6.5 (standard deviation 4.1).²¹ However, NCS are invasive; can be mildly painful for the patient; require expertise and time to administer; and can only detect TIPN once it has progressed to the point that there is functional impairment of large peripheral nerves; these problems make it less preferable for the routine clinical evaluation for TIPN-like symptoms.²² Other functional assays besides NCS have been investigated. Sudomotor testing is a novel technique that uses the topical administration of acetylcholine to measure the sweat response that is mediated by the small fibers of peripheral nerves. Although non-invasive, sudomotor testing tends to have wide variability which can make interpretation difficult and it has not yet been tested in chemotherapy-induced peripheral neuropathy. A nerve excitability study is a novel non-invasive functional assay that detects the threshold of current that is needed to elicit an action potential. Similar to US, this experimental technique has been shown that it can detect oxaliplatin-induced peripheral neuropathy;²³ but has not yet been studied for TIPN.

Skin biopsies are able to detect TIPN with good diagnostic sensitivity that may be superior to NCS in chronic TIPN.²⁴ Measurement of the intraepidermal nerve fiber (IENF) density is a standard clinical assessment used in the evaluation of peripheral neuropathies. Healthy control participants have an average IENF density of 21.1 (standard deviation 10.4) at the thigh and 13.8 (standard deviation 6.7) in the distal leg.^{25,26} Typical IENF density findings in TIPN include reduced nerve fiber density that is typically more pronounced distally at the lower leg (mean 3.0, range 0.5-6.3) as compared to the thigh (mean 5.5, range 0.7-13.2).²⁷ As expected, the IENF density likely continues to decrease with continued exposure to chemotherapy and worsening neuropathy, as a small longitudinal study of patients receiving oxaliplatin found that the distal leg IENF density progressively decreased from baseline 15.39 (6.75) to 12.89 (4.73) at 6 months to 9.45 (3.92) at 12 months.²⁸ However, IENF density has not been shown to be predictive of chemotherapy-induced peripheral neuropathy and, similar to NCS, skin biopsies are invasive and may be mildly painful.

The inflammatory mechanism by which TIPN causes neurotoxicity is poorly understood. Mast cells may have a role in the pathophysiology of some other types of chemotherapy-induced peripheral neuropathy. A mouse study found that prevention of mast cell degranulation by a congenital mast cell deficiency or administration of a mast cell stabilizer could prevent oxaliplatin neuropathy.²⁹ Mast cell markers can be detected in serum and increased number or atypia of mast cells can be detected on skin biopsy.

Given the lack of a consensus approach to the diagnosis of TIPN, further research is needed to better characterize TIPN that ideally uses non-invasive methods to facilitate serial measurements if they are needed. The accurate assessment of TIPN allows for appropriate adjustment of taxane chemotherapy dosing and potential improvement of clinical outcomes in breast cancer patients. This pilot study will assess the utility of ultrasound as a novel technique to assess TIPN.

2.0 Objectives

2.1 Primary Objectives

2.1.1 To compare tibial motor nerve ultrasound CSA between TIPN patients and historical data among healthy adults.

2.2 Secondary Objective

2.2.1 To compare sural sensory nerve ultrasound CSA between TIPN patients and historical data among healthy adults.

2.2.2 To determine if the above changes in nerve CSA correlate with NCS changes in the same TIPN patients.

2.2.3 To determine if the above changes in nerve CSA correlate with changes on a self-reported neuropathy scale (QLQ-CIPN20) in the same TIPN patients.

2.2.4 To determine if the above changes in nerve CSA correlate with IENF density changes on skin biopsy in the same TIPN patients.

2.3 Exploratory Objectives

2.3.1 To assess activated mast cells in skin biopsies in TIPN patients in relation to severity of symptoms and above findings.

2.3.2 To assess serum inflammatory markers in TIPN patients in relation to severity of symptoms and above findings.

3.0 Study Population

This study is designed to enroll breast cancer patients with clinically documented symptoms consistent with TIPN.

3.1 Inclusion Criteria

- Breast cancer (any stage).
- Previously or currently receiving taxane-based chemotherapy.
- Clinical symptoms of peripheral neuropathy noted in medical record and suspected to be secondary to taxane-based therapy.
- Ability and willingness to understand and sign an informed consent.

3.2 Exclusion Criteria

- Self-reported or documented history of pre-existing peripheral neuropathy prior to initiation of taxane chemotherapy.
- Male patients.
- Unable to provide history.

3.3 Inclusion of women and minorities

3.3.1 Women of all races and ethnicity who meet the above-described eligibility criteria are eligible for this trial.

3.3.2 The study consent form will also be provided in Spanish for Spanish-speaking participants. Male patients will be excluded as the frequency of breast cancer among males is low and the frequencies needed to treat men for male breast cancer are currently unknown; therefore, 100% of participants to be women. We plan to enroll at least 20% Black or African American (N=4). Because of the low incidence among American Indian/Alaska Native, Asian, and Hispanic/Latino women in our catchment area, we do not expect accruals of individuals of those ancestries; however, no ancestry background is being excluded. Should we not meet or exceed these estimates, the PI will engage the Cancer Center Health Equity Advisory Group to discuss strategies to enhance recruitment in these target populations.

4.0 Methods

4.1 Registration Procedures

All patients entered on any WFBCCC trial, whether treatment, companion, or cancer control trial, **must** be linked to a study protocol in EPIC within 24 hours of Informed Consent. Patients **must** be registered prior to the initiation of treatment.

You must perform the following steps in order to ensure prompt registration of your patient:

1. Complete the Eligibility Checklist (Appendix A)
2. Complete the Protocol Registration Form (Appendix B)
3. Complete the Ethnicity Verification Form (Appendix C)
4. Alert the Cancer Center registrar by phone, *and then* send the signed Informed Consent Form, Eligibility Checklist and Protocol Registration Form to the registrar, either by fax or e-mail.

Contact Information:

Protocol Registrar [contact]

Protocol Registrar [contact]

Protocol Registrar E-MAIL ([contact])

*Protocol Registration is open from 8:30 AM - 4:00 PM, Monday-Friday.

5. Fax/e-mail ALL eligibility source documents with registration. Patients **will not** be registered without all required supporting documents.

Note: If labs were performed at an outside institution, provide a printout of the results. Ensure that the most recent lab values are sent.

To complete the registration process, the Registrar will:

- assign a patient study number
- register the patient on the study

A Pilot Study Using Ultrasound for the Detection of Taxane-Induced Peripheral Neuropathy
Wake Forest Baptist Comprehensive Cancer Center (WFBCCC)
CCCWFU # 97217

4.2 Study Activities

Study Calendar*				
	Encounter 1	Encounter 2	Encounter 3	Follow-up: 30 days to confirm adequate healing of biopsy
Informed Consent	X			
Medical history (Appendix C)		X		
Physical exam		X		
QLQ-CIPN20 ^f		X		
Blood draw ^{c,f}		X		
Abbreviated Neurologic Exam ^a			X	
Nerve Conduction Study ^b			X	
Ultrasound ^d			X	
Skin Biopsies ^e			X	
Follow-up skin assessment				X

* The Study Calendar represents an ideal schedule for the completion of study related activities; however, depending on patient and physician availability, the completion of these clinical tasks may occur at any clinical encounter. ***The exceptions to this rule are following: the informed consent should be signed before any research activity occurs, and the blood draw and the QLQ-CPIN20 should be performed on the same day. While all study related tasks may be completed at a single visit, it is anticipated that due to scheduling, at least 2 study visits will be required.

a: exam to include strength assessment of the tibialis anterior and gastrocnemius and deep tendon reflex exam of the Achilles on the limb to be examined with NCV and US.

b: Sural and Tibial nerve assessments

c: Green top heparin tube: 12 ml blood sample

d: Sural and Tibial nerve assessments

e: Two skin biopsies will be obtained as 4mm punch biopsies at distal end of leg in sural nerve territory (10cm above lateral malleolus) and from the thigh

f: The blood draw and the QLQ-CIPN20 should be performed on the same day.

4.3 Study setting

Enrollment of participants will be take place at WFBMC Comprehensive Cancer Center (CCC) outpatient clinics.

4.4 Enrollment (Encounter 1)

Recruitment information will be posted in the CCC outpatient clinics in the rooms where breast cancer patients are treated. Study investigators will also review medical records and work with WFBMC clinicians to identify patients who would potentially meet inclusion criteria. If a breast cancer patient expresses interest in enrollment on the study, a study investigator or research employee will meet the patient in clinic to ensure that they are eligible and to obtain consent for enrollment on the study. We anticipate an accrual rate of 1-2 participants per month. This is feasible because 242 breast cancer patients received taxanes (52% paclitaxel, 45% docetaxel) in 2016 at the WFBCCC alone and with additional breast cancer patients treated at the Clemmons satellite office.

4.5 Clinical assessment (Encounter 2)

Clinical assessment will take place in the CCC outpatient clinic and will include a focused history by one of the study investigators or research employees. The medical

A Pilot Study Using Ultrasound for the Detection of Taxane-Induced Peripheral Neuropathy
Wake Forest Baptist Comprehensive Cancer Center (WFBCCC)
CCCWFU # 97217

record will also be reviewed to confirm details of the medical history. The focused history will assess age, body-mass index (BMI), breast cancer staging, types and dosages of chemotherapy received, corticosteroid and analgesic use, and presence of comorbidities (diabetes, B12 deficiency, thyroid disorders, alcoholism, depression, carpal tunnel syndrome, sciatica). . A physical examination will occur to document strength and reflexes. The QLQ-CIPN20 questionnaire will also be administered at this encounter.

In most cases, blood testing will be added on to regularly scheduled phlebotomy for clinical labs which are drawn as part of routine oncology care. Some participants may require an additional blood draw if insufficient blood samples were collected. For the purposes of our study, 12mL of venous blood will be collected in a sodium heparin (green-top) collection tube and then transferred directly to [name] lab for processing.

Blood Sample Preparation

1. Email notification will be sent to [name] ([contact]), [name] ([contact]) and [name] ([contact]) the day before the blood collection.
2. Blood will be collected in two green-top vacutainer tubes containing heparin (60 USP Units of Lithium Heparin/6ml tube), and immediately inverted 8-10 times to prevent coagulation.
Attention: Protocol #: CCCWFU # (97217) and the ORIS PID in addition to the other standard information should be on the tube.
3. Samples will then be transported from the Cancer Center to the [name] lab (Lab: [name], [name], Office: [name]).

4.6 Diagnostic testing (Encounter 3)

Participants will be referred to Diagnostic Neurology clinic for and abbreviate neurological exam to assess strength of the tibialis anterior and gastrocnemius and deep tendon reflex exam of the Achilles tendon on the limb to be examined in nerve conduction studies and ultrasound evaluation during this encounter. Further, a skin biopsy will be obtained. These tests will be completed at a single visit and no further follow-up with neurology is required as part of the study protocol. All of these studies are considered standard clinical tests for the evaluation of peripheral neuropathy and sensory neuropathy. Patients will receive a Visa gift card upon completion of the neuropathy assessment.

Peripheral nerve US technique and reference values for the sural sensory (measured at the ankle) and tibial motor nerves are based on institutional data and standard institutional practice. These reference values were de-identified historical data which have also been published by Cartwright et al.(2008) ⁸ as noted in the Introduction and Background section. Peripheral nerves will be assessed at non-compressive sites with a routine 15Hz linear probe. If available, a higher resolution 70Hz linear probe may be used – this would allow for descriptive characterization of nerve changes and would not

A Pilot Study Using Ultrasound for the Detection of Taxane-Induced Peripheral Neuropathy
Wake Forest Baptist Comprehensive Cancer Center (WFBCCC)
CCCWFU # 97217

be anticipated to cause variability in terms of CSA measurement as compared to the standard 15Hz US.

NCS technique and reference values for the sural and tibial nerves among healthy adults are based on data from Chen et al. (2016) and standard institutional practice³⁰. NCS assessment of the sural sensory nerve involves electrode placement at the ankle (posteroinferior to the lateral malleolus) and more distally with a 3cm bar for a distance of approximately 14cm; the nerve is stimulated at the calf midline with a display sensitivity 2-5 uV/div and sweep of 1 ms/div. The sural sensory nerve reference values for amplitude is a lower limit (3rd percentile) of 4 uV (onset-to-peak) and 4 uV (peak-to-peak); and for latency is an upper limit (97th percentile) of 3.6 ms (onset) and 4.5 ms (peak). NCS assessment of the tibial motor nerve involves electrode placement at the medial foot (slightly anterior/inferior to the navicular tubercle) and more distally at the first metatarsophalangeal (MTP) joint for a distance of approximately 8cm; the nerve is stimulated at the ankle (posterior to the medial malleolus) and knee (at the midpopliteal fossa) with a display sensitivity 5 mV/div and sweep of 5 ms/div. The tibial motor nerve reference values for distal amplitude is a lower limit (3rd percentile) of 4.4 mV across all ages; and for distal latency is an upper limit (97th percentile) of 6.1 ms.

Two skin biopsies will be obtained as 4-5mm punch biopsies at distal end of leg in sural nerve territory (10cm above lateral malleolus) and in the upper thigh. As described in a review by Lauria and Devigili (2007),³¹ biopsied tissue will be cut into 50 uM sections which will be hematoxylin and eosin stained and also immunostained with an antibody to PGP (protein gene product) 9.5, a neuron- and neuroendocrine cell-specific ubiquitin carboxy-terminal hydrolase expressed throughout the peripheral nervous system. Slides will be reviewed by Dermatopathology ([name] and/or [name]) in order to count PGP9.5-positive fibers as they cross the dermal-epidermal junction to calculate linear density of IENF (IENF/mm). Additional staining will be done as indicated. Routine processing of specimens and comparison to standardized values (similar to those described by McArthur et al.(1998))²⁵ will be done by Dermatopathology as per their institutional guidelines. These methods are standard clinical procedures for the routine assessment of IENF density. Dermatopathology will also obtain descriptive measures of morphologic changes that will be analyzed as an exploratory outcome. Additional unstained slides or blocks will be stored and transferred to [name] lab for staining and testing of mast cell concentration, tryptase, chymase and histamine. The results will be recorded on Appendix E for transfer into REDCap.

Storage of Serum and Skin Biopsy Material

Venous blood will be stored in lab refrigerator prior to transfer (in oncology lab) and after transfer (in [name] lab). Serum and left over skin biopsy material from patients will be stored in [name] laboratory in the Department of Cancer Biology until use.

Tests Using Serum

Serum testing for inflammatory markers will be performed using commercially available kit that may include but not be limited to ELISA and will be performed according to the

manufacturers' instructions and modified accordingly if needed given the type of sample and/or target of interest to be detected. Data resulting from these experiments may be kept in laboratory notebooks or in on the data sheets provided in Appendix C.

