Appendix H: Ultrasound Nerve Diameter Data Form

ORIS PID: _____	Date Completed: ___ / ___ / ___
PI: [name]., [name]. Study Number: CCCWFU 97217	

To be used for determination of tibial and sural nerve diameters.

Date of Procedure: ___ / ___ / ___

SAGITTAL VIEW

Nerve and Side	Probe Location and Landmark	Max/Min #1	Max/Min #2	Max/Min #3	Mobility	Echo	Vasc	Other

SEGMENTS SCREENED

Nerve and Side	Axial segments imaged	Sagittal segments imaged

LEGEND

Echogenicity = scores include N (normal), INC (increased), DEC (decreased), or A (absent)
Axial/Sagittal Motion = describes nerve motion with passive or active flexion of relevant joint: scores include N , INC , DEC , A
Vascularity = describes presence of vascular activity within nerve
Other = Includes Persistent Median Artery (PMA), Bifid Nerve, Trifid Nerve, FDS in CTS, etc.

Person recording information: _____

A Pilot Study Using Ultrasound for the Detection of Taxane-Induced Peripheral Neuropathy
 Wake Forest Baptist Comprehensive Cancer Center (WFBCCC)
 CCCWFU # 97217

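### Nothing in the protocol keeps the ultrasound operator from knowing the NCS, examination and QLQ-CIPN20 results when measuring CSA, so the secondary correlations with CSA could be inflated

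*Combined protocol and SAP*

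**What the plan says.** Section 4.6 refers participants to Diagnostic Neurology for a strength check and "deep tendon reflex exam of the Achilles tendon on the limb to be examined in nerve conduction studies and ultrasound evaluation during this encounter", plus skin biopsy, and adds: "These tests will be completed at a single visit". Footnote a to the calendar in 4.2 likewise ties the examination to the scanned limb: "exam to include strength assessment of the tibialis anterior and gastrocnemius and deep tendon reflex exam of the Achilles on the limb to be examined". The calendar rows for Encounter 3 run neurological examination, NCS, ultrasound, biopsies. The calendar is described as an ideal, however, and "the completion of these clinical tasks may occur at any clinical encounter". The only constraints are consent before any research activity, and blood draw and QLQ-CIPN20 on the same day.

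The calendar places the QLQ-CIPN20 at Encounter 2, and 4.5 also documents strength and reflexes there, so these results would normally exist before the scan.

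The protocol does not say who scans. Appendix H has a line for "Person recording information"; Appendix I asks for a neurologist's initials. Appendix H has columns for three Max/Min readings per site, and no rule for combining them is given.

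Objective 2.2.2 reads: "To determine if the above changes in nerve CSA correlate with NCS changes in the same TIPN patients". Objective 2.2.3 asks the same for the QLQ-CIPN20. Section 6.3 uses Spearman's coefficient, then a general linear model with CSA as the dependent variable.

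**The concern.** The two objectives ask whether CSA agrees with other measures of neuropathy. The answer is informative only if CSA is measured without knowledge of those measures. Measuring a nerve by ultrasound involves judgement about where to place the probe and where the nerve boundary lies, and repeat readings with no combining rule add more. The background also gives a reader a direction to lean: section 1.0 reports enlargement in diabetic polyneuropathy, and 6.1.1 cites a mean tibial increase of 5.3 in a similar comparison.

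If known results pull the CSA reading, a correlation can appear where none exists, or a modest one can look strong. No analysis of the collected data could separate the two. The study is meant to assess the utility of ultrasound in TIPN, and agreement with established measures is a large part of what it can show.

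**Working it through.** **1. What the documents settle and what they leave open**

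| Question | Documents |
|---|---|
| Same limb for examination, NCS and ultrasound? | Yes (4.6; 4.2 footnote a) |
| Same visit? | Planned in 4.6; relaxed by the 4.2 calendar note |
| Order within the visit? | Not fixed. Calendar rows put NCS before ultrasound. The technique text in 4.6, the form list in 7.0 and the order of Appendices H and I put ultrasound before NCS |
| Who measures CSA? | Not stated |
| Masking or independent reading of CSA? | None in the text |

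So the route to bias is open, but the documents do not show that it is taken.

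**2. The plan's own figure**

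Section 6.1 gives no power or precision for the correlations. Its primary claim is unaffected: 3.2/4.4 = 0.727 SD, and a two-sided two-sample t-test of 22 against 60 at 0.05 has 82.2% power, in line with the stated more than 80%. Masking would not change it.

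**3. How sensitive a correlation at n = 22 is to reader expectation**

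Inputs from 6.1.1: n = 22, tibial CSA SD 4.4 mm². Assumption: the reading shifts by b mm² for each SD of NCS abnormality. The documents give no value for b, so a range is shown. True correlation is set to zero.

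Model: CSA = 4.4·z₁ + b·z₂, where z₂ is NCS abnormality and z₁, z₂ are independent standard normals.

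Induced Pearson correlation: r = b / √(4.4² + b²).

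Expected sample Spearman coefficient under normality: E(rho) = [6 / (π(n + 1))] × [arcsin r + (n − 2)·arcsin(r/2)].

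For b = 1.0: r = 1.0/√(19.36 + 1.00) = 0.222. Then E(rho) = [6/(π × 23)] × [0.2235 + 20 × 0.1110] = 0.0830 × 2.444 = 0.20.

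Two-sided 5% critical value at n = 22, from the t approximation on 20 degrees of freedom (t = 2.086): 2.086/√(20 + 2.086²) = 0.423. Rejection rates are from 100,000 simulated studies per row.

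| Assumed b (mm² per SD of NCS) | r | Mean rho | Share with \|rho\| > 0.423 |
|---|---|---|---|
| 0 (masked) | 0 | 0.00 | 5% |
| 0.5 | 0.113 | 0.10 | 8% |
| 1.0 | 0.222 | 0.20 | 15% |
| 1.5 | 0.323 | 0.30 | 28% |

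With NCS amplitude in place of abnormality the sign reverses and the size is the same. The arithmetic applies equally to the QLQ-CIPN20 if b is read as the shift per SD of that score.

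**The case against.** - **Order and operator.** A reader might infer from the calendar that the operator scans after seeing the NCS. The documents do not support that. Row order is not an instruction, other parts of the protocol list ultrasound first, and the scanner may be a different person from the neurologist doing the NCS. This stands, and it limits the point to what the protocol fails to prevent.
- **Expectation.** The background is mixed. The one chemotherapy ultrasound study cited in 1.0 found no sural abnormality, the text says no TIPN ultrasound data exist, and the primary test is two-sided. This weakens the case for a strong expectation but does not remove it.
- **Magnitude.** The simulation returns the bias that was put in. This also stands. The table shows how sensitive a 22-patient correlation is, not how large any bias will be. Section 6.3 attaches no decision rule to these correlations, so the shift in rho matters more than the rejection rate.
- **Incomplete masking.** Participants enter with documented symptoms and can describe them during the scan. Test results and scores can be withheld; the patient's complaints cannot. Scanning first also leaves the NCS operator free to know the CSA unless that is addressed separately.

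None of this supplies a safeguard that the protocol contains.

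**Conclusion.** The point holds in a limited form. The protocol does not prevent the CSA reader from knowing the NCS, examination and QLQ-CIPN20 results, and this leaves the correlations under 2.2.2 and 2.2.3 open to inflation. The size is unknown. Under the assumed shifts of 0.5 to 1.5 mm² per SD of NCS abnormality, with no true correlation, mean rho is about 0.10 to 0.30 and nominal significance occurs in about 8% to 28% of studies.

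Two stronger readings are not supported. The first is that CSA will in fact be read with the results known: neither operator nor sequence is specified. The second is that masking to these results would protect the primary comparison. Every scanned patient is a known case and the controls are historical, so expectation about case status remains whatever the order of tests.

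The change is worth making because it is cheap and closes a route to bias that cannot be corrected after data collection.

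**What to change.** In 4.6, with a matching footnote to the calendar in 4.2, state that:

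- ultrasound is done first within Encounter 3, and tibial and sural CSA are recorded and dated on Appendix H before the Encounter 3 neurological examination and NCS begin;
- where NCS, QLQ-CIPN20 or the Encounter 2 strength and reflex findings already exist, the ultrasound operator does not open them until CSA is recorded.

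The single-visit sentence in 4.6 and the any-encounter note in 4.2 should be reconciled at the same time. Appendix H should be checked for a place to enter CSA, since its stated purpose is "To be used for determination of tibial and sural nerve diameters"; the layout may have been lost in text extraction.

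Cost: a short addition to 4.6 and a footnote, and less freedom in ordering tests within the visit. No extra staff or procedure is needed, and the sample size is unchanged. The patient's own complaints remain unmasked, which the report should acknowledge.
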